#### Patient and disease characteristics

- 1. Age > 18 years at the time of screening
- 2. Histologically or pathologically confirmed invasive SCC (or histologic variant) of the oral cavity, oropharynx (p16 positive, negative, or unknown), hypopharynx, larynx, unknown primary, paranasal sinuses, or nasal cavity.

a. In situations in which the patient fulfills all other inclusion criteria but the biopsy shows SCC in-situ or moderate/severe dysplasia (without definitive evidence of invasive SCC), but the patient is scheduled to undergo curative intent surgery by the treating oncologic surgeon due to clinical suspicion of invasive SCC, the diagnosis of SCC-in situ or moderate/severe dysplasia is sufficient to full the pathologic diagnosis enrollment criterion.

3. American Joint Committee on Cancer (AJCC) clinical stage grouping III-IV (8th edition) for patients with SCC of the oral cavity, p16-negative oropharynx, hypopharynx, larynx, paranasal sinuses, and nasal cavity; or AJCC clinical stage grouping III-IV (7th edition) for patients with p16-positive SCC of the oropharynx or unknown primary.

a. At screening, AJCC clinical stage grouping should be determined based on a combination of physical exam, diagnostic evaluation with cross sectional imaging of the neck (computerized tomography (CT) and/or magnetic resonance imaging (MRI)) and/or 18-F-fluoro-deoxyglucose positron emission tomography (FDG PET) CT within 30 days

b. In situations in which the patient fulfills all other inclusion criteria but the biopsy shows SCC in-situ or moderate/severe dysplasia (without definitive evidence of invasive SCC), but would otherwise have an appropriate clinical stage grouping as defined in criterion 5, the diagnosis of SCC-in situ or moderate/severe dysplasia is sufficient to full the staging enrollment criterion.

4. No prior exposure to radiation therapy, with or without concurrent chemotherapy, for treatment of HNSCC in the definitive or adjuvant therapy settings

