# 8 STUDY ASSESSMENTS AND PROCEDURES

#### 8.1 ENDPOINT AND OTHER NON-SAFETY ASSESSMENTS

#### Primary Endpoint

Initiation of postoperative PORT > 6 weeks after surgery is defined as more than 42 calendar days from the time of the definitive surgical resection to the initiation of radiation therapy. In situations in which the surgical management of the primary tumor and the neck are staged (i.e. occur on two different calendar days), the date of the surgery for the primary tumor will be used. In situations in which an additional surgical resection is required (e.g. re-resection of positive margins to clear residual disease), the date of the earlier (i.e. attempted definitive) surgical procedure will be used to determine the target start date for PORT.

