#### Secondary Endpoints Clinical Outcomes

Racial disparities in initiation of PORT > 6 weeks after surgery is defined as the difference in the rate of initiation of PORT > 6 weeks after surgery between white and AA HNC patients.

Days between surgery and the start of PORT is defined as the time, in days, between the date of definitive surgical resection to the initiation of radiation therapy. All of the criteria used to adjudicate the date of the definitive surgical procedure described for the primary outcome measure will be applied to this measure.

Barriers resolved is the number of barriers identified by the navigator that are resolved during the NDURE intervention, as determined by the navigator log.

Unresolved barriers is the number of barriers identified by the navigator that are not resolved during the NDURE intervention, as determined by the navigator log.

Pre-Surgical Radiation Consultation is defined as the attendance by the patient at a consultation with a radiation oncologist (at MUSC or elsewhere) prior to surgery to discuss RT in the definitive or adjuvant setting

Pre-Radiation Therapy Dental Extractions is defined as the extraction of teeth prior to discharge from the index hospitalization for the definitive surgical procedure. Patients who are edentulous are not evaluable for this measure.

Surgery to Pathology Report </= 7 days is defined as the production of the pathology report from the definitive surgical procedure within the EMR within 7 calendar days of the definitive surgical procedure. Addenda to the pathology report at the request of the HNC team (e.g. tumor p16 status) are not counted in this measure.

Surgery to PORT Referral </= 10 days is defined as the placement of a referral for PORT, at MUSC or elsewhere, within 10 calendar days of the definitive surgical procedure.

RT Referral to Consult </= 10 days is defined as the evaluation of the patient at a postoperative consultation with a radiation oncologist within 10 calendar days of the referral being placed (or postoperative appointment being scheduled in cases in which care has been established and the return visit is no longer a consultation). The consultation may occur in the clinic or the hospital depending upon clinical circumstances.

RT Consult to Initiation </= 21 days is defined as the initiation of PORT within 21 calendar days of the patient being evaluated by a radiation oncologist for PORT.

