# Covariates

Behavioral Risk Factor Surveillance Survey (BRFSS) Demographics. The BRFSS is the nation's premier health-related survey that collects data about health-related risk behaviors from US residents. The demographic section from the BRFSS will be used (in-person) to ascertain participant sex, age, race, marital status, insurance, educational attainment, living situation, zipcode, phones for personal use, employment, and annual household income.

BRFSS Tobacco Use and Alcohol Consumption. The tobacco use and alcohol consumption sections of the BRFSS will be used (in-person) to characterize total cigarette exposure, current cigarette use, quit attempts, days of alcohol consumption, average drinks/day, frequency of  $\geq$  5 drinks, and maximum number of drinks.

Clinical and Oncologic Characteristics. Clinical characteristics will include comorbid medical conditions, and cancer history. Oncologic characteristics will include HNC tumor subsite, HNC tumor histology, p16/human papillomavirus (HPV) tumor status, American Joint Committee on Cancer TNM Class and overall stage grouping, type of ablative surgery, type of reconstruction, treatment dates, facility of planned adjuvant therapy, and adjuvant treatment type planned (adjuvant radiation or chemoradiation).

Barrier Load Survey will measure 1) the number of barriers identified in the BRP during NDURE; and 2) the type of barrier in our modified version of existing PN logs

Cultural Factor Survey is a validated, psychometrically sound questionnaire consists of three subscales assessing temporal orientation (5 items), collectivism (6 items), and religiosity (9 items). Prior PN studies have used these scales to measure cultural factors.

MD Anderson Symptom Inventory-Head Neck (MDASI-HN) is a validated, psychometrically sound, 28-item multisymptom patient-reported outcome measure for clinical and research use that assesses the severity of symptoms experienced by patients with cancer (including 9 HNC-specific symptoms), and the associated interference with daily living caused by these symptoms. Higher scores indicate more severe symptom/symptom interference.

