# 9.4 STATISTICAL ANALYSES

# 9.4.1 GENERAL APPROACH

We will construct graphical displays and calculate descriptive statistics (e.g. frequencies and percent for categorical variables, and mean, median, standard deviation, and range for continuous variables). Covariates will be specified below. For inferential tests, we will use a p-value of 0.05, two-sided, and 95% confidence intervals (CIs) to assess statistical significance (Type I error). Normality of the data will be assessed before underlying statistical procedures will be performed. We will evaluate variable transformations as needed to satisfy assumptions and consider transformations of variables to induce approximate normality and stabilize variance as needed. Nonparametric tests will be applied when appropriate.

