# 9.4.3 ANALYSIS OF THE SECONDARY ENDPOINT(S)

We will analyze time-to-PORT as a continuous variable and estimate median time-to-PORT for the cohort overall and for AA and white subgroups using Kaplan-Meier curves with Greenwood variance estimation for the corresponding 95% Cls. We will calculate racial disparities in time-to-PORT by comparing the difference in median time-to-PORT between white and AA patients.

We will compare the findings from our phase II trial of NDURE (rate of PORT delay; median time-to-PORT for the cohort overall and for racial disparities in each endpoint) to historical controls (at MUSC and nationally) using Fisher's exact test. If the upper bound of the 95% CI for the rate of delayed PORT (and racial disparities in delayed PORT) is at or below the lower bound of the 95% CI for the similar endpoint in our historical controls, we can conclude that the preliminary estimates of the therapeutic activity of NDURE (i.e. clinical benefit) suggest that further rigorous testing of the efficacy of the PN intervention in a larger clinical trial is warranted based on these phase II results. We will nevertheless interpret findings relative to historical control cautiously given that the data do not arise from a randomized trial.

For the secondary endpoints of barrier reduction and unresolved barriers, we will calculate the proportion of unresolved barriers and the frequency of unresolved barriers (respectively) at the end of NDURE, consistent with prior PN studies. We will use logistic regression to assess the relationship between unresolved barriers and the rate of PORT delay (primary endpoint), controlling for covariates listed in **Section 8.1**.

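### The adjusted logistic model linking unresolved barriers to PORT delay cannot be fitted with the covariates it names (about 36 items, 45 patients); if they are only a candidate pool, the adjustment set is not pre-specified.

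*Combined protocol and SAP*

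**What the plan says.** Section 9.4.1 announces that "Covariates will be specified below". For the model relating unresolved barriers to delay, the only later specification is in Section 9.4.3: "We will use logistic regression to assess the relationship between unresolved barriers and the rate of PORT delay (primary endpoint), controlling for covariates listed" under Section 8.1.

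Section 8.1 has a part headed Covariates. Its demographic block ends with "educational attainment, living situation, zipcode, phones for personal use, employment, and annual household income". Its oncologic block includes "type of ablative surgery, type of reconstruction, treatment dates, facility of planned adjuvant therapy". Its barrier-load entry includes "the number of barriers identified in the BRP during NDURE". Tobacco and alcohol use, cultural subscales and a symptom inventory are listed as well.

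Two definitions elsewhere in Section 8.1 matter here. The exposure, unresolved barriers, "is the number of barriers identified by the navigator that are not resolved during the NDURE intervention". The outcome, delay, is "more than 42 calendar days from the time of the definitive surgical resection to the initiation of radiation therapy".

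Section 9.4.3 has one covariate-selection rule, a screen at p < .10. It is worded for linear regressions in which the dependent variable is the pre-post change in a theoretical-construct measure.

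**The concern.** A model with nearly as many parameters as patients can usually separate delayed from non-delayed patients perfectly. Maximum likelihood then has no finite estimates, and the software returns a warning or meaningless odds ratios. The analyst would have to drop covariates after seeing the data, and the plan gives no rule for doing so.

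Two items on the list raise a further problem of content. Treatment dates that cover surgery and the start of radiation determine the outcome. Identified barriers are the sum of resolved and unresolved barriers. With that count in the model, the odds ratio compares patients with the same barrier burden but different resolution; without it, total burden is mixed in.

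At stake is the one stated model linking unresolved barriers to delay, in a pilot of a barrier-focused intervention that is meant to inform a larger trial.

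**Working it through.** **The plan's own figures.** No sample-size or power figure is given for this model. Section 9.2 justifies n = 45 by precision alone, and that figure reproduces: 1.96 × √(0.25/45) = 0.146, stated as 0.15.

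**Counting the covariates (Section 8.1).** 11 demographic + 7 tobacco/alcohol + 12 clinical/oncologic + 2 barrier load + 3 cultural + 1 symptom = 36. The total is 35 to 37 depending on whether TNM class and stage, or symptom severity and interference, are counted separately.

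**Parameters against patients.** With one term per item: 36 + exposure + intercept = 38 parameters for 45 patients. The smaller outcome group is at most 22, so there are at most 22/37 ≈ 0.6 patients in it per slope. One term per item is generous. Section 5.1 admits tumours of the "oral cavity, oropharynx (p16 positive, negative, or unknown), hypopharynx, larynx, unknown primary, paranasal sinuses, or nasal cavity", which is seven subsites and three p16 states. Without dates, and with indicators for those two items only: 35 + 5 + 1 + exposure + intercept = 43 parameters.

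**Cover's formula for complete separation.** For 36 predictors plus intercept and 45 points in general position: 2^(−44) × Σ C(44, i), i = 0 to 36, = 0.999997.

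**Simulation.** Separation was checked by linear programming in 500 datasets per setting, with n = 45 and delay rates of 20–50% (9, 14, 18 or 22 delayed). Assumptions, since the documents give no distributions: unresolved barriers Poisson with mean 0.3, 1 or 4; covariates unrelated to outcome, about half binary and half continuous, one term each.

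| Covariates besides unresolved barriers | Complete separation | Any separation |
|---|---|---|
| 35 (list without dates) | 100% | 100% |
| 30 | 99.4–100% | 99.6–100% |
| 25 | 89–100% | 89–100% |
| 20 | 39–95% | 39–96% |
| 12 | 0–13% | 1–32% |
| 6 (one per instrument or data block) | 0% | 0.2–20% |
| 3 | 0% | 0–13% |

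Pairwise covariate correlation of 0.3 or 0.6 leaves the 35-covariate row at 100% complete separation. A separate run with 37 predictors gave 100% at delay rates from 10% to 56%, the last being the historical rate in Section 2.2.

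**Pool reading.** Suppose the p < .10 screen were borrowed. With 35 unrelated, independent covariates the number admitted is Binomial(35, 0.10): mean 3.5, 95% range 0 to 7. The adjustment set would be partly chance.

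**A short model.** Unresolved barriers plus race (15 of 45), care fragmentation (51%, Section 2.2) and a two-category insurance variable (30% in the risk category, assumed; 20–40% tried), with 400 datasets in each of 24 settings and Poisson means 0.3 to 4. Any separation occurred in 0–5% of datasets at 30–50% delay and 3–18% at 20% delay. Firth regression converged in 9,599 of 9,600. Its 95% CI reaches a factor of 4.5 (mean 0.3, 20% delay) down to 1.4 (mean 4, 50% delay) either side of the per-barrier odds ratio. Unadjusted, the factor is 4.1 to 1.4. With identified barriers added (resolved barriers Poisson with mean 4, assumed) it is 4.9 to 1.6.

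**The case against.** The strongest reply is that nobody would enter the whole list. Section 8.1 describes data to be collected, including zipcode and telephones, and an analyst would pick a sensible handful. On that reading the model can be fitted, and the defect is an unnamed subset, common in pilot protocols. The study also disclaims definitive conclusions, and no decision rule uses this odds ratio.

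The limited weight stands, and so does the likelihood that a subset would be used in practice. But the sentence in Section 9.4.3 is an instruction, and it fails if followed. Departing from it means choosing covariates with the outcome in hand, because the only screening rule belongs to other models.

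A second objection concerns the remedy. Section 9.4.7 plans analyses by age and sex too, Section 2.2 names travel distance as associated with delay, and Section 2.1 lists treatment toxicity and finances as barriers, so other short sets are defensible. That stands: race, insurance and fragmentation are an example.

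Third, few delays would strain even the short model. Further simulations gave any separation in 13–27% of datasets with 7 delayed patients and 31–50% with 5. This is a fair warning about precision. Firth estimates stay finite under separation, and the unadjusted odds ratio gives a simpler estimate to fall back on.

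**Conclusion.** The concern holds. As written, the model cannot be fitted by ordinary maximum likelihood: about 38 parameters at one per item, 45 patients, and complete separation in all simulated datasets with 35 covariates. As a candidate pool, its adjustment set is not pre-specified. The first conclusion needs only the item count and the sample size; the simulated percentages for smaller models, and the interval widths, rest on the assumed distributions above.

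The reach is narrow. The descriptive primary estimate, the counts and proportions of barriers, and the comparison with historical controls are untouched. The correction should be made, but it does not put the trial's main result in doubt.

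**What to change.** In Section 9.4.3, replace the reference to the Section 8.1 list with two or three named single-parameter covariates.

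- **Covariates.** For example, race (a study objective), insurance status in two categories, and care fragmentation; Section 9.4.7 already plans analyses of the primary endpoint by the last two. Give reasons for omissions. Travel distance would have to be derived from zipcode, and no analysis by it is planned. For age and sex, Section 9.4.7 itself says that historical data have not established an association with delay.
- **Method.** Fit by a penalised method such as Firth logistic regression, and report the unadjusted odds ratio alongside.
- **Excluded and overlapping items.** State that treatment dates are not covariates. State whether the number of identified barriers stays in; if it does, the odds ratio describes non-resolution at a given barrier burden.

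The cost is two or three sentences and no new data. The price is that residual confounding is acknowledged rather than nominally adjusted for, and the estimate will still be imprecise if unresolved barriers or delays are rare.

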# 4 STUDY DESIGN

### 4.1 OVERALL DESIGN

We will conduct a single-site, single-arm phase II clinical trial of NDURE among HNC patients undergoing surgery and PORT (n=45; AA n=15; white n=30). NDURE is a theory-based, multi-level PN intervention consisting of three in-person, clinic-based sessions of manualized PN with multiple intervention components that target system- (care coordination), interpersonal- (social support), and individual- (HBM; perceived susceptibility, severity, barriers, self-efficacy) level health behavior theoretical constructs to reduce barriers to care, increase HNC care delivery, and improve clinical outcomes (timely, equitable PORT). NDURE will be delivered from surgical consultation to PORT initiation (~3 months). The three in-person NDURE navigation sessions, which are expected to take 30-60 minutes each, will coincide with the presurgical consult, hospital discharge, and 1st postoperative clinic visit, time points chosen to facilitate case identification and coordination across key care transitions. Measures of PORT delay will be analyzed overall (primary outcome) and for racial differences (secondary outcome). Measures of the preliminary clinical impact of NDURE on PORT barrier reduction and delivery of key HNC care processes will be collected (secondary outcome), feasibility (secondary outcome; accrual rate, NDURE completion rate, PN caseload), acceptability (secondary outcome; satisfaction with PN). Measures of the theoretical constructs underlying the multi-level, theory-based NDURE intervention will be compared pre- and post-intervention. Post-intervention qualitative work with patients and providers will help refine NDURE.

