Secondary endpoints for feasibility, acceptability, fidelity and HNC care delivery will be analyzed as follows. For study accrual, we will calculate the proportion and frequency of eligible patients who accrue (overall, white, and AA). Given its pilot nature, the study is not designed to evaluate racial differences in accrual, although reasons for study decline will be collected, analyzed by race, and used to refine recruitment. NDURE completion will be analyzed as 1) the percentage of enrolled patients who attend all three in-person NDURE sessions and 2) the proportion of three in-person NDURE sessions that are completed. For navigator caseload, we will consider the frequency of simultaneous cases navigated. Navigator time allocation for direct and indirect time, as well as patient-report measures of satisfaction with navigation (acceptability) will be summarized as described above for continuous data. NDURE fidelity will be analyzed as the proportion of enrolled patients who have a BRP documented in the EMR. For HNC care delivery processes, we will calculate the proportion of patients receiving each key HNC care delivery process.

For secondary endpoints evaluating the theoretical constructs underlying NDURE (care coordination, support, perceived susceptibility, severity, barriers, and self-efficacy), we will estimate the mean change in each measure (pre-post) as well as standard deviations and 95% CIs for each; comparisons will be conducted using Wilcoxon sign-rank test. Baseline levels of each dependent variable will be controlled in each model; additional covariates will be considered by examining associations between potential covariates and each dependent variable using linear regression (p < .10 where the change in each outcome measure is the dependent variable). This method will allow estimation of intervention effects while adjusting for potential confounders.

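### Section 9.4.3 claims confounder-adjusted intervention effects from a pre-post model that, in a single-arm trial, can give only the average change

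*Combined protocol and SAP*

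**What the plan says.** Section 4.1 sets the design: "We will conduct a single-site, single-arm phase II clinical trial of NDURE among HNC patients undergoing surgery and PORT", with 45 patients (15 AA, 30 white). Section 6.3, on randomization and blinding, is marked not applicable.

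For the constructs behind the behavioural-mechanism objective, Section 9.4.3 sets out these steps:

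- Estimate: "we will estimate the mean change in each measure (pre-post) as well as standard deviations and 95% CIs for each".
- Test: "comparisons will be conducted using Wilcoxon sign-rank test".
- Adjustment: "Baseline levels of each dependent variable will be controlled in each model".
- Further covariates: "additional covariates will be considered by examining associations between potential covariates and each dependent variable using linear regression", with the criterion "p < .10 where the change in each outcome measure is the dependent variable".
- Claimed result: "This method will allow estimation of intervention effects while adjusting for potential confounders".

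The candidate covariates for this screen are not listed, and the form of the adjusted model is not given. The historical controls in Sections 9.1 and 9.4.3 are used for PORT delay and time-to-PORT, not for the construct scores.

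**The concern.** The last sentence gives the regression a property that the design cannot supply. An intervention effect needs a contrast between NDURE and something else, and confounding needs an exposure that differs between patients. Neither exists here.

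The flow diagram places the baseline questionnaires at Visit 1 and the follow-up at Visit 5. Surgery, recovery and the approach to radiotherapy lie between. Social support, perceived susceptibility, severity, barriers and self-efficacy could all move over that period without any navigation. A report following the plan could present such a movement as an NDURE effect from which confounding had been removed. That would affect the conclusion on the mechanism objective and what is carried into the planned cluster-randomized trial.

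**Working it through.** **The plan's own figures.** Section 9.2 gives precision only for the PORT delay rate. Its figure reproduces (1.96 × √(0.25/45) = 0.146, stated as 0.15) but has no bearing here. The plan gives no number for the construct analyses.

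**Step 1: is an intervention term estimable?** Regress change on an intercept, an NDURE indicator, baseline and three covariates. Every patient has indicator value 1, so that column duplicates the intercept. In a worked example with n = 45 the design matrix has 6 columns and rank 5. The NDURE coefficient is not estimable.

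**Step 2: what does the adjusted estimate equal?** In least squares, intercept = mean change − Σ(slope × covariate mean). With every covariate centred, each covariate mean is 0, so the intercept is the mean change whichever covariates are chosen. In the same example both were 0.2677. Uncentred, the intercept is only a prediction at covariate value zero (3.06 in that example). Neither form separates NDURE from time.

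**Step 3: what happens when NDURE does nothing?** Simulation with n = 45, zero NDURE effect, a time trend common to all patients, pre-post correlation 0.5 (assumed), and 10 or 20 noise candidates screened at p < .10:

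| True time trend | Average adjusted estimate | Runs significant at 5% |
|---|---|---|
| 0.3 SD | 0.30 | about 64% |
| 0.5 SD | 0.50 | about 95% |

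The adjustment removes none of the trend.

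**Step 4: is a test of the centred intercept valid as a test of change?** Let ρ be the pre-post correlation, with equal variances before and after. The squared correlation of change with baseline is (1 − ρ)/2. The regression standard error uses the residual variance, so it is smaller than the true standard error of the mean change by the factor √((1 + ρ)/2). With 43 degrees of freedom the critical value is 2.017, and actual rejection under no change is about 2 × P(t > 2.017 × factor):

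| ρ (assumed) | Factor | Effective cut-off | Rejection, baseline only |
|---|---|---|---|
| 0.3 | 0.806 | 1.626 | 11% |
| 0.5 | 0.866 | 1.747 | 8.8% |
| 0.7 | 0.922 | 1.859 | 7.0% |

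Simulation at ρ = 0.5 gave 8.6–8.8% with baseline only, then 9.6% (10 noise candidates) and 10.6% (20) after the screen.

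**Step 5: how often does the screen select noise?** With k independent candidates unrelated to change, the expected number selected is 0.1k, and P(at least one) = 1 − 0.9^k for each outcome. The value of k is an assumption. The covariate part of Section 8.1 holds roughly 35 individual variables, so the range runs from 5 to 35:

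| k | Expected | P(at least one) |
|---|---|---|
| 5 | 0.5 | 41% |
| 10 | 1.0 | 65% |
| 20 | 2.0 | 88% |
| 35 | 3.5 | about 97% |

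**The case against.** The strongest reply is that the plan already leads with the right quantity. The within-patient mean change with its 95% CI comes first in Section 9.4.3, and Section 4.1 describes the comparison as before versus after the intervention. This stands. A reader might infer that the mechanism objective would rest only on something the design cannot provide, but the documents do not support that. The fault lies in the adjusted model and the sentence describing it.

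The plan is also openly preliminary. Section 4.2 says that the design does not aim to establish efficacy, and Section 9.4.3 urges caution about historical controls. These statements lower the stakes, but neither qualifies the sentence on adjusted effects.

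Four stronger readings should be resisted:

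- **The signed-rank test is meant to carry the adjustment.** The plan does not say so. It names that test for the pre-post comparison and refers to models separately.
- **The screen badly distorts the result.** It does not bias the centred estimate, and it adds only about 1–2 percentage points of rejection beyond baseline adjustment. The noise-selection probabilities assume independent candidates, whereas income, insurance and education are plausibly correlated. Covariates are also only to be considered, and baseline is included regardless of the screen.
- **All candidates are fixed characteristics.** Symptom severity and barrier load are measured at Visits 1 to 5 and could partly track the course of treatment. The plan does not specify using them that way, and doing so would still not isolate NDURE.
- **A comparison arm exists.** Section 9.3 refers to randomization to NDURE or Usual Care. That text must be reconciled with Sections 4.1 and 6.3, but no Usual Care arm is described and nothing provides construct scores for one.

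**Conclusion.** The claim of confounder-adjusted intervention effects is wrong as written. That conclusion follows from the single-arm design and needs no numerical assumption: the model has no intervention contrast, and its centred intercept is the raw mean change.

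The secondary fault is that testing this intercept with the ordinary regression standard error is too liberal. Rejection is about 9% with baseline alone and 10–11% after the screen, at ρ = 0.5 with 10–20 noise candidates. The baseline-only figure runs from 7% to 11% for ρ from 0.7 down to 0.3. This matters only if the intercept is tested, and the plan does not say whether it will be.

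The significant results in Step 3 are not in themselves false findings of change, because the scores really did shift. The error is attributing the shift to NDURE. The consequence is moderate, since these are secondary endpoints in a pilot, but it bears directly on what can be said about mechanism.

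**What to change.** In Section 9.4.3:

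1. Delete the sentence on estimating intervention effects while adjusting for confounders.
2. Keep the planned within-patient mean change with 95% CI and the signed-rank test as the sole estimate and test of change. Label the result *pre-post change, not attributable to NDURE alone*.
3. If the regression is kept, call it an exploratory analysis of predictors of change. Replace the p < .10 screen with a short pre-specified covariate list; which covariates to include is for the study team to decide. State that the intercept will be neither tested nor reported as an effect.

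This needs only a wording change, with no extra patients, data or visits. The downside is a more modest claim.
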